5. RESEARCH OBJECTIVES

- 1) To compare plasma levels, biopsy mRNA (using low density expression arrays) and protein (using either Luminex or Western blotting) levels of the following parameters between IBD patients treated with Frondanol and those treated with placebo at baseline and after six months of treatment:
 - a) Cytokines: TNF α , IL1 β , IL6, IL17A, IL21, IL22, IL23, IFN γ , IFN α , as well as vascular endothelial growth factor (VEGF-A), MIP-1, MIP-2;
 - b) Markers of inflammation: Myeloperoxidase, calprotectin, S100A12, β 2-microglobulin, amyloid A (A-SAA), intercellular adhesion molecule 1 (ICAM-1), vascular cell adhesion molecule 1 (VCAM-1), MIP-2 α (CXCL2), MCP-1 (CCL2). Leukotriene B4 (LTB4), 5-hydroxyeicosatetraenoic acid (5-HETE) and prostaglandin E2 (PGE2) will be measured by specific ELISA assays.
- 2) To compare the following routine clinical parameters between IBD patients treated with Frondanol and those treated with placebo at baseline and after six months of treatment:
 - a) Patient symptoms;
 - b) Blood: Complete blood count (CBC), erythrocyte sedimentation rate (ESR), C-reactive protein (CRP), albumin;
 - c) Stool: Fecal calprotectin level;
 - d) Endoscopic and histologic features.
- 3) To compare in-vitro concentration-dependent responses to Frondanol and placebo on inflamed organoids by measurement of cytokines and other inflammatory markers, in particular 5-HETE, LTB4 and PGE2.

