6.3 Sample and recruitment

All eligible IBD patients visiting Gastroenterology Department of any of the study centres that will participate in patient recruitment (Mediclinic City Hospital, Mediclinic Parkview Hospital and Rashid hospital) under the care of any of the coinvestigator consultant gastroenterologists during the period of recruitment (12 months from the start date of the study – to be decided following ethical approval) will be offered to take part in the study.

Block randomization over four blocks of 25 patients will be used to ensure an equal number of patients in each treatment group, even if the trial was terminated early for any reason. Two blocks will be reserved for patients with quiescent/minimal disease and two blocks for patients with mild disease, in order to ensure an equal number of these patients in each treatment group. Patients will be randomised (1:1) to receive Frondanol (one 1000 mg capsule twice daily) or placebo (in a similar capsule) as an adjunct to their standard therapy using a randomization number sequence generator. This will be conducted by the study statistician using the Microsoft Excel random number generator and will only be shared with the study coordinator.

All patients and investigators, excluding the study coordinator, will be blinded to treatment allocation. Frondanol and placebo capsules will be placed in identical-looking vials which will be labelled with the study name and number, and no identifying information. The labelling of the vials will be done with the open randomization sheet by the study coordinator. When a patient agrees to participate, and signs the informed consent form, the physician will assign to the patient the next available randomization number from the randomization sheet (supplied by the study coordinator) with the corresponding labelled medication vial. Patients will be instructed to take one capsule of their assigned medication twice daily. Hence, capsules will be given in a double-blind manner where patient and physician are not aware of treatment allocation as the treatment and placebo vials will only indicate the pilot study name. Investigators involved in the laboratory analysis of samples will also be blinded, they will only know if a patient belongs to group 1 or 2 but will not know which group is taking Frondanol and which is taking placebo.

RJ

Version 3.2. Effective Date: 04 December 2021

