6.5 Eligibility criteria

- **Inclusion criteria:**

A confirmed clinical diagnosis of IBD of any duration, age 18 years or older, with mild to moderate disease and on standard therapy. The diagnostic criteria for IBD include the presence of chronic diarrhoea for more than four weeks, and evidence of active inflammation on endoscopy and chronic changes on biopsy. Patients with stable mild to moderate IBD will be eligible for the study. Stable IBD is defined as having stable symptoms over a period of several weeks, diagnostic evaluation has been completed and the patient has been on consistent medication. Mild to moderate IBD is indicated by a Partial Mayo score (Mayo Clinic Score/Disease Activity Index for Colitis) of between 1-6, and a total of Mayo score of 1-10 (Pabla and Schwartz, 2020). For patients with Crohn's disease, only those with Crohn's colitis will be included (patients with small bowel disease are eligible to enter the trial as long as they also have large bowel inflammation).

- **Exclusion criteria:**

Pregnancy, breastfeeding, allergy to seafood or marine products, severe medical illness such as uncontrolled diabetes ($\text{HbA1C}>10$), significant or unstable cardiovascular or pulmonary disease, impaired renal function ($\text{Cr}>2.0\text{mg/dL}$), current or recent (<1 year) malignancy, or other significant medical illness that in the view of the investigators may impair participation in the study. Patients with severe IBD (defined by a Partial Mayo score of 7-9 and a total Mayo score of 11-12 (Pabla and Schwartz, 2020), with active symptoms) will not be eligible to participate in the study.

Reference:

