6.14 Study schedule

Table 1: Variables to be collected from participants

Method of data collection	Variables
Questionnaires	Mayo Score, IBDQ
Medical record	Symptoms
Blood samples	Routine blood tests as well as an extra sample (10 mL) for research purposes will be obtained at T0 (start of study), T1 (3 months) and T2 (6 months).
Stool samples	Routine stool sample will be collected for measurement of fetal calprotectin levels at the recruiting hospital at T0, T1 and T2.
Tissue samples	Colonoscopies will be performed as part of the routine clinical practice and these include acquisition of routine biopsies, typically 10-15 from each patient. A few additional biopsies (2-4) will be collected for our studies during routine colonoscopies when these are performed, then they will be snap frozen and analyzed in MBRU research laboratory facilities.

Table 2: Schedule of Activities

Variable	Visit # 1 (T0)	Visit # 2 (T1 – 3months)	Visit # 3 (T2 – 6 months)
Questionnaires	Mayo Score, IBDQ	Mayo Score, IBDQ	Mayo Score, IBDQ
Medical record	Symptoms	Symptoms	Symptoms
Blood samples	Routine blood tests as well as an extra sample (10 mL) will be obtained, stored and analyzed in MBRU research laboratory facilities.	Routine blood tests as well as an extra sample (10 mL) will be obtained, stored and analyzed in MBRU research laboratory facilities.	Routine blood tests as well as an extra sample (10 mL) will be obtained, stored and analyzed in MBRU research laboratory facilities.
Stool sample	Routine stool sample will be collected for measurement of fetal calprotectin levels at MCH	Routine stool sample will be collected for measurement of fetal calprotectin levels at MCH	Routine stool sample will be collected for measurement of fetal calprotectin levels at MCH
Tissue samples	If colonoscopy is performed for routine clinical practice at the start of the study, a few additional biopsies (2-4) will be collected for our studies, snap frozen and analyzed in	No tissue samples collected	If colonoscopy is performed for routine clinical practice at the end of the study, a few additional biopsies (2-4) will be collected for our studies, snap frozen and analyzed in

RJ

Version 3.2. Effective Date: 04 December 2021

	MBRU research laboratory facilities.	MBRU research laboratory facilities.
--	--------------------------------------	--------------------------------------

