8.2 Statistical methods

All statistical analyses will be carried out using SPSS Software (Armonk, New York, USA). Potential confounders such as age and sex will be controlled for during the analysis phase. A per-protocol analysis including only participants who have a full data set will be used to assess the efficacy of Frondanol treatment in lowering inflammatory markers. An intention-to-treat analysis will also be conducted including patients who drop out before the study ends, for whom we will use last observation carried forward (LOCF) i.e. we will impute the last observed data for all subsequent (missing) observation points. For quantitative data, within-group and between-group comparisons will be analyzed using the General linear Repeated Model (MANOVA), which would allow for adjustment of potential confounders such as age and sex. Data will be plotted as mean \pm SEM and p values <0.05 will be considered statistically significant.

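### Section 8.2 plans a repeated-measures GLM/MANOVA without naming the treatment contrast, the T0 term or the stratum; a T0-adjusted 6-month difference would settle the contrast, usually with more power

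*Combined protocol and SAP*

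**What the plan says.** Section 8.2 gives one sentence on the model: for quantitative data, "within-group and between-group comparisons will be analyzed using the General linear Repeated Model (MANOVA", a method "which would allow for adjustment of potential confounders such as age and sex". The significance threshold is p<0.05. The analysis sets are a per-protocol set ("A per-protocol analysis including only participants who have a full data set will be used") and an intention-to-treat set that fills in dropouts by last observation carried forward (LOCF).

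The objectives in section 5 compare Frondanol patients with "those treated with placebo at baseline and after six months of treatment". That gives two time points but no contrast.

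Section 6.14 schedules three visits: blood samples "will be obtained at T0 (start of study), T1 (3 months) and T2 (6 months"), with stool samples and questionnaires at the same visits. The T1 entry for tissue is "No tissue samples collected", and biopsies at T0 and T2 depend on a routine colonoscopy taking place.

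On randomisation, section 6.3 says: "Two blocks will be reserved for patients with quiescent/minimal disease and two blocks for patients with mild disease". Section 6.5 says: "Patients with stable mild to moderate IBD will be eligible for the study". The analysis section does not mention the stratum.

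**The concern.** A repeated-measures GLM with three visits produces several tests that could each be called the between-group comparison: a group main effect averaged over visits, a 2-df group-by-time test, and contrasts at or between single visits. They answer different questions and differ in power. The main effect includes T0, where randomisation makes the expected difference zero, so a real effect is diluted.

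Two things are at stake. If no test is named, the contrast can be picked once results are visible, and p<0.05 no longer means a 5% error rate. And if T0 is used only as one level of the response, the analysis may give up precision that data already scheduled could supply. For tissue, with T0 and T2 only, group-by-time is the same test as the T2-minus-T0 change.

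**Working it through.** **Inputs from the documents.** 50 per arm, 1:1 (sections 6.3, 6.4); p<0.05 (section 8.2; two-sided is assumed, as sidedness is not stated); visits T0, T1, T2, and tissue at T0 and T2 only (section 6.14). Section 8.1 is headed as a power calculation but gives no effect size, SD or power, so the 100 patients cannot be reproduced.

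**Assumed inputs.** True difference 0.5 SD at T2 (T2 SD = 1); T1 effect full (0.5), half (0.25) or zero; T0–T2 correlation r from 0.3 to 0.8. The base case has equal SDs and the same correlation between all visits (compound symmetry).

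**Variance per patient and degrees of freedom**
- T2 ANCOVA on T0: 1 − r², 97 df.
- Change, with k = SD(T2)/SD(T0): 1 + 1/k² − 2r/k, 98 df. At k = 1 this is 2(1 − r).
- Main effect (mean of three visits): (1 + 2r)/3, 98 df, with expected difference (0 + T1 effect + 0.5)/3.
- Group-by-time: Hotelling test on (T1−T0, T2−T0), 2 and 97 df.

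**Example, r = 0.5, k = 1** (standard error = √(2 × variance/50))
- ANCOVA: √(2 × 0.75/50) = 0.173; 0.5/0.173 = 2.89.
- Change: √(2 × 1/50) = 0.200; 0.5/0.200 = 2.50.
- Main effect, full T1 effect: √(2 × 0.667/50) = 0.163; 0.333/0.163 = 2.04. With zero T1 effect: 0.167/0.163 = 1.02.

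**Power (%) from noncentral t and F, equal SDs, compound symmetry**

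| Test | r=0.3 | 0.5 | 0.7 | 0.8 |
|---|---|---|---|---|
| T2 ANCOVA | 73.7 | 81.5 | 93.4 | 98.5 |
| T2−T0 change | 55.3 | 69.7 | 89.2 | 97.5 |
| Group-by-time, T1 full or zero | 56.6 | 72.2 | 91.8 | 98.6 |
| Group-by-time, T1 half | 44.5 | 58.9 | 81.9 | 94.6 |
| Main effect, T1 full | 61.8 | 52.4 | 45.4 | 42.6 |
| Main effect, T1 zero | 20.4 | 17.3 | 15.2 | 14.4 |

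**ANCOVA against change in general.** Change variance minus ANCOVA variance is (1 + 1/k² − 2r/k) − (1 − r²) = (r − 1/k)². This is never negative, and it is zero when rk = 1, that is, when the slope of T2 on T0 is 1. With k = 1 the variance ratio is (1 − r²)/(2(1 − r)) = (1 + r)/2. At r = 0.5 the gain varies with k:

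| k | Variance ratio | ANCOVA power | Change power | Gain (points) |
|---|---|---|---|---|
| 0.8 | 0.75/1.3125 = 0.57 | 81.5 | 58.0 | about 24 |
| 1.0 | 0.75/1.00 = 0.75 | 81.5 | 69.7 | about 12 |
| 1.25 | 0.75/0.84 = 0.89 | 81.5 | 77.1 | about 4 |
| 1.5 | 0.75/0.778 = 0.96 | 81.5 | 80.1 | about 1 |

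**Tissue with fewer pairs.** With 25 pairs per arm (assumed), k = 1 and r = 0.3/0.5/0.7, ANCOVA has 44/52/68% and change 31/41/61%.

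**Where ANCOVA does not win.** If correlation decays with time (AR(1)) and the T1 effect is full or zero, group-by-time overtakes ANCOVA above an adjacent-visit correlation of about 0.67: 82.9 against 81.0% at 0.7, and 94.8 against 89.6% at 0.8. With a half T1 effect it has 58.0 and 74.1%. With a full T1 effect under compound symmetry, the main effect beats ANCOVA below r of about 0.15 (81.6 against 69.7% at r = 0).

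**Choosing the test afterwards.** Two independent 5% tests give 1 − 0.95² = 9.75%. Null simulation (40,000 runs per r, compound symmetry) gives 9.7–9.9% for the better of main effect and group-by-time, and 12.0–12.3% if change is added.

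**The case against.** The strongest reply is that only one sentence is missing. Group-by-time and change are valid tests, section 5 pairs baseline with six months and so points towards change over time, and the covariate list is given by example, so T0 and stratum are not ruled out. All of that stands. A reader might infer that the planned model is invalid, or that T0 and stratum are excluded; the text supports neither. They are unspecified, and a 2-df group-by-time test stated in advance would be acceptable.

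Second, a reader might take (1 + r)/2 as a general efficiency gain. It needs equal SDs at T0 and T2. Section 6.5 admits stable disease within a bounded Mayo range, so a wider spread at T2 is plausible, at least for that score, and the gain could then be close to nil.

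Third, for blood, stool and questionnaires the natural planned test is the 2-df group-by-time test, not the 1-df change, and it can beat ANCOVA. This limits the efficiency argument but not the need to name the test.

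Fourth, the 10% error rate describes deliberate picking between two tests. The documents do not show that this is intended, only that nothing prevents it.

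Fifth, it would be wrong to say that the planned tissue test uses only patients with both biopsies. That fits the per-protocol set; under LOCF, a dropout with only a T0 biopsy would enter with T2 set equal to T0.

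**Conclusion.** The point holds as a recommended improvement, not as an error that invalidates the plan. Section 8.2 leaves the treatment contrast open, and the candidates differ widely: at r = 0.5 under the base assumptions, power runs from 17% (main effect, no effect yet at T1) to 82% (T2 ANCOVA). Two conclusions do not depend on the assumed values: the main effect averages in a visit with no expected difference, and change is never more efficient than T2 ANCOVA on T0, apart from one degree of freedom. The size of the gain over change does depend on them: about 18/12/4/1 points at r = 0.3/0.5/0.7/0.8 with equal SDs, and about 24 down to 1 at r = 0.5 as the SD ratio goes from 0.8 to 1.5. No effect size, SD or correlation is in the documents.

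No figure is claimed for the stratum: its prognostic strength is not given, and a constant stratum effect cancels in change and in group-by-time.

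A reader might infer that naming the contrast ends selective reporting. It does not. Two analysis sets and a long marker list with no stated primary remain.

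**What to change.** In section 8.2, name the T0-adjusted 6-month between-group difference with 95% CI as the treatment result for each quantitative endpoint, and specify:

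- **Blood, stool, questionnaires:** model T1 and T2 as responses, with treatment, visit, treatment-by-visit, T0 value, T0-by-visit, randomisation stratum, age and sex, and an unstructured covariance (for example SPSS MIXED). T0 then leaves the response vector. Keep T0-by-visit: with complete data and before stratum, age and sex are added, the T2 contrast then equals T2 ANCOVA, whereas a single common T0 slope departs from it.
- **Tissue:** T2 ANCOVA on the T0 value and stratum, with the number of biopsy pairs per arm reported.
- **Within-group changes:** descriptive only.
- **Analysis set:** state which set carries this result and how it relates to the planned per-protocol and LOCF intention-to-treat analyses. For tissue, a complete-pair analysis differs from the LOCF one, so this is a decision and not just wording.
- **Stratum:** enter it as used at randomisation. Sections 6.3 (quiescent/minimal and mild) and 6.5 (mild to moderate) must be reconciled so that every eligible patient has a stratum.

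If the effect at 3 months also matters and a 2-df group-by-time test is preferred, state that now instead.

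The cost is the wording of section 8.2, the reconciliation of the strata and a few degrees of freedom. About 95 remain if nobody drops out, and fewer for tissue and the per-protocol set. No new data are needed: T0 values for blood, stool and questionnaires are already scheduled. The primary marker and multiplicity need their own decisions.

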Planned Size of Sample (if applicable)	100 patients (50 per arm) with stable IBD will be recruited into this pilot study.
Follow up duration (if applicable)	Six months
Planned Study Period	Two years
Research Question/Aim(s)	
1) To compare plasma levels, biopsy mRNA (using low density expression arrays) and protein (using either Luminex or Western blotting) levels of the following parameters between IBD patients treated with Frondanol and those treated with placebo at baseline and after six months of treatment:
 
a) Cytokines: TNFα, IL1β, IL6, IL17A, IL21, IL22, IL23, IFNγ, IFNα, as well as vascular endothelial growth factor (VEGF-A), MIP-1, MIP-2;
 
b) Markers of inflammation: Myeloperoxidase, calprotectin, S100A12, β2-microglobulin, amyloid A (A-SAA), intercellular adhesion molecule 1 (ICAM-1), vascular cell adhesion molecule 1 (VCAM-1), MIP-2α (CXCL2), MCP-1 (CCL2). Leukotriene B4 (LTB4), 5-hydroxyeicosatetraenoic acid (5-HETE) and prostaglandin E2 (PGE2) will be measured by specific ELISA assays.
 
2) To compare the following routine clinical parameters between IBD patients treated with Frondanol and those treated with placebo at baseline and after six months of treatment:
 
a) Patient symptoms;
 
b) Blood: Complete blood count (CBC), erythrocyte sedimentation rate (ESR), C-reactive protein (CRP), albumin;
 
c) Stool: Fecal calprotectin level;
 
d) Endoscopic and histologic features.
 
3) To compare in-vitro concentration-dependent responses to Frondanol and placebo on inflamed organoids by measurement of cytokines and other inflammatory markers, in particular 5-HETE, LTB4 and PGE2.

RJ

Version 3.2. Effective Date: 04 December 2021

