6. STUDY DESIGN/METHODOLOGY

5.1 Design overview

This is a pilot, prospective, double-blinded, two-arm, randomized controlled trial of the efficacy of Frondanol in comparison to placebo in decreasing bowel inflammation in patients with a clinical diagnosis of IBD who are in remission and on standard of care treatment.

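### Section 8.2 names no primary endpoint and applies p<0.05 to every comparison; with an inert product, the chance of at least one nominally significant favourable biomarker is about 16–50% at moderate assumed correlations, against 2.5% for one pre-specified test

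*Combined protocol and SAP*

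**What the plan says.** Section 8.2 gives the decision rule as "p values <0.05 will be considered statistically significant". It ties the per-protocol analysis to the trial's purpose: that analysis is to be "used to assess the efficacy of Frondanol treatment in lowering inflammatory markers", so the markers are treated as a class and none is singled out. It then adds a second analysis set: "An intention-to-treat analysis will also be conducted including patients who drop out before the study ends". The model for quantitative data is the "General linear Repeated Model (MANOVA), which would allow for adjustment of potential confounders such as age and sex", used for both within-group and between-group comparisons.

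Section 5.1 calls the study a "randomized controlled trial of the efficacy of Frondanol in comparison to placebo". Objective 1 in section 5 covers plasma levels, "biopsy mRNA (using low density expression arrays) and protein (using either Luminex or Western blotting) levels of the following parameters", followed by two marker lists and three lipid mediators measured by ELISA. Objective 2 adds symptoms, blood tests, fecal calprotectin, endoscopy and histology. Neither objective ranks its measures. Both fix the timing: "at baseline and after six months of treatment".

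Section 8.1 is headed as a sample size and power calculation but repeats recruitment and randomisation text, so no primary endpoint can be inferred from it.

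**The concern.** When many markers are each tested at 0.05 and none is named in advance as the one that answers the question, a product with no effect can readily yield at least one marker labelled statistically significant in the favourable direction. The plan does not tell a reader whether such a marker was the intended test or the best of several dozen.

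Timing matters too. A primary endpoint protects against selection only if it is chosen before results are seen by group, and section 6.3 lets laboratory investigators know whether a patient is in group 1 or group 2.

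**Working it through.** **There is no figure in the plan to reproduce.** The documents state no family-wise error rate. The sample size of 100 (50 per arm) comes without an effect size, SD or power.

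**Number of comparisons (objective 1, section 5).**
- List (a): TNFα, IL1β, IL6, IL17A, IL21, IL22, IL23, IFNγ, IFNα, VEGF-A, MIP-1, MIP-2 = 12.
- List (b) without the lipid mediators: myeloperoxidase, calprotectin, S100A12, β2-microglobulin, A-SAA, ICAM-1, VCAM-1, MIP-2α (CXCL2), MCP-1 = 9.
- Matrices: plasma, biopsy mRNA, biopsy protein = 3.
- ELISA markers: LTB4, 5-HETE, PGE2 = 3, counted once each.
- Total: (12 + 9) × 3 + 3 = 66. If MIP-2 and MIP-2α are one analyte: (12 + 8) × 3 + 3 = 63.
- Extreme case of no biopsies, assuming the ELISA markers are measured in plasma: 21 + 3 = 24, or 20 + 3 = 23.

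The documents conflict on how much tissue there will be. Table 2 (section 6.14) takes biopsies only if a routine colonoscopy is performed. Section 6.13 has all patients complete a baseline and a six-month endoscopy. Section 6.2 only hopes that colonoscopies can be timed this way. The no-biopsy count is therefore a floor, not an expectation.

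The counts leave out objective 2, the in-vitro work, the three-month visit, within-group tests and the second analysis set.

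**Chance of at least one favourable p<0.05 with no true effect.** Sidedness is not stated. Two-sided tests are assumed, so 0.025 lies in the favourable direction for each test.

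- Expected number of favourable nominal hits: 66 × 0.025 = 1.65; 24 × 0.025 = 0.6.
- Independent tests: 1 − 0.975^m. For m = 66, 0.812; for 63, 0.797; for 24, 0.455; for 23, 0.441.
- Common correlation ρ between test statistics: 1 − ∫ Φ((1.96 − √ρ·t)/√(1−ρ))^m φ(t) dt, by numerical integration.

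The documents give no correlations, so every ρ is an assumption.

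| Tests | ρ = 0 | 0.3 | 0.5 | 0.7 | 0.8 | 0.9 |
|---|---|---|---|---|---|---|
| 66 | 81% | 50% | 35% | 22% | 16% | 10% |
| 63 | 80% | 49% | 34% | 22% | 16% | 10% |
| 24 | 46% | 31% | 23% | 16% | 12% | 8% |
| 23 | 44% | 30% | 23% | 15% | 12% | 8% |
| 1 | 2.5% | 2.5% | 2.5% | 2.5% | 2.5% | 2.5% |

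A simulation of 100,000 replicates agrees: 34.4% and 10.4% for 66 tests at ρ = 0.5 and 0.9, and 23.3% and 8.0% for 24 tests.

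The 16–50% range runs from 24 tests at ρ = 0.7 (15.6%) to 66 tests at ρ = 0.3 (49.9%). Using 23 tests moves the lower end to 15%.

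**With adjustment.** With Benjamini-Hochberg at 0.05 across the panel, the simulated chance of at least one favourable rejection is about 1–3% for 24 or 66 tests over the same correlations.

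**The case against.** The best defence is that this is a pilot, and the documents say so repeatedly. A pilot may screen many markers without a confirmatory claim. That lessens the consequence, but the plan does not use this defence: it labels nothing exploratory, section 5 contains no feasibility objective that could be the main aim instead, and sections 5.1 and 8.2 speak of efficacy and statistical significance.

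A second defence is that MANOVA is a joint test. Section 8.2 does not say whether markers enter the model together or one at a time. It presents the model as a repeated-measures analysis with adjustment for age and sex. No joint test is described as a gate to the individual markers, so protection across markers cannot be assumed.

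Four stronger readings are tempting and are not supported:
- **That the risk is 81%.** That needs all 66 tests and zero correlation, which is hard to defend for plasma, mRNA and protein readings of related markers in the same patients. The 8% end is just as extreme in the other direction.
- **That these are chances of a false efficacy conclusion.** The plan does not say that one significant marker would establish efficacy.
- **That a hit in either analysis set counts.** Section 8.2 ties efficacy to the per-protocol set and adds intention-to-treat alongside it. It never states an either-set rule, though it also does not say which result prevails if they differ.
- **That no biopsies will be available.** Section 6.13 says otherwise. Resolving the conflict in its favour moves the count towards 66.

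**Conclusion.** The concern holds. No primary endpoint, testing order, multiplicity rule or exploratory label appears in the documents, while p<0.05 applies without restriction in an analysis meant to assess efficacy. At assumed correlations of 0.7 to 0.3, the chance that an inert product yields at least one nominally significant favourable marker is roughly 6 to 20 times the 2.5% of a single pre-specified test (15.6/2.5 = 6.2; 49.9/2.5 = 20). Even the most lenient case shown, 24 tests at 0.9, gives about three times that figure (8.1/2.5 = 3.2).

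The sizes rest on two-sided testing, a common correlation between test statistics and a literal count of objective 1. The omission itself rests on none of these. It should be corrected before outcomes are seen by group.

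**What to change.** Make the change before anyone sees outcomes by group, including the laboratory staff who know group 1 or 2.

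1. In sections 5 and 8.2, name one primary endpoint, compared between groups at six months in one named analysis set. Reserve p<0.05 as a significance claim for that test. This is the essential part.
2. Label the biomarker panel and the remaining measures secondary or exploratory. Report them with 95% confidence intervals and preferably Benjamini-Hochberg-adjusted p-values.
3. Do not use within-group p-values as evidence of efficacy.

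Fecal calprotectin is one candidate, because it is scheduled at T0, T1 and T2 and needs no colonoscopy. If it is chosen, reconcile where it is measured: Table 1 says the recruiting hospital and Table 2 says MCH. It would also move the lead question from objective 1 to objective 2, and the investigators may prefer an objective 1 marker.

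If they want no primary endpoint, the alternative is to declare all comparisons exploratory and remove the significance and efficacy wording.

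The cost is a decision on endpoint and analysis set plus protocol text, with no new visits or samples. The downside is that fewer markers will be called significant, and a real effect on a non-primary marker would be reported as exploratory only. Missing-data handling and the withdrawal wording in sections 6.8 and 6.10 are separate issues.
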